9.2.3. Assessment of Severity

The Investigator must determine the severity of the event according to the criteria below and the Investigator's clinical judgment. Severity describes the intensity of the AE.

Grade 1	Mild; asymptomatic or mild symptoms; clinical or diagnostic observations only; or intervention not indicated
Grade 2	Moderate; minimal, local, or non-invasive intervention indicated; or limiting age-appropriate instrumental activities of daily living
Grade 3	Severe or medically significant, but not immediately life-threatening; hospitalization or prolongation of hospitalization indicated; disabling; or limiting self-care activities of daily living
Grade 4	Life-threatening consequence or urgent intervention indicated
Grade 5	Event resulted in death

9.2.4. Procedures for Recording AEs

Investigators should use correct medical terminology/concepts when recording AEs on the AE eCRF. Avoid colloquialisms and abbreviations. Only 1 AE term should be recorded in the event field on the AE eCRF.

All AEs spontaneously reported by the patient and/or in response to an open-ended question from study personnel or revealed by observation, physical examination or other diagnostic procedures will be recorded on the appropriate forms in the eCRF.

Only 1 AE term should be recorded in the event field on the AE eCRF. When possible, a unifying diagnosis, or signs and symptoms indicating a common underlying pathology should be noted as 1 comprehensive event. For example, the combination of general malaise, mild fever, headache, and rhinitis should be described as a “common cold” rather than listing each symptom separately.

9.2.4.1. Diagnosis versus Signs and Symptoms

A diagnosis (if known) should be recorded on the AE eCRF rather than individual signs and symptoms (e.g., record only liver failure or hepatitis rather than jaundice, asterixis, and elevated transaminases; record tumor lysis syndrome rather than hypocalcemia, hyperkalemia, hyperuricemia, etc.). However, if a constellation of signs and/or symptoms cannot be medically characterized as a single diagnosis or syndrome at the time of reporting, each individual event should be recorded on the AE eCRF. If a diagnosis is subsequently established, all previously reported AEs based on signs and symptoms should be nullified and replaced by 1 AE report based on the single diagnosis, with a starting date that corresponds to the starting date of the first symptom of the eventual diagnosis.

9.2.4.2. Adverse Events that are Secondary to Other Events

In general, AEs that are secondary to other events (e.g., cascade events or clinical sequelae) should be identified by their primary cause, with the exception of severe or serious secondary events. A medically significant secondary AE that is separated in time from the initiating event should be recorded as an independent event on the AE eCRF. For example:

- If vomiting results in mild dehydration with no additional treatment in a healthy adult, only vomiting should be reported on the eCRF.
- If vomiting results in severe dehydration, both events should be reported separately on the eCRF.
- If a severe gastrointestinal hemorrhage leads to renal failure, both events should be reported separately on the eCRF.
- If dizziness leads to a fall and consequent fracture, all 3 events should be reported separately on the eCRF.
- If neutropenia is accompanied by an infection, both events should be reported separately on the eCRF.

All AEs should be recorded separately on the AE eCRF if it is unclear as to whether the events are associated.

9.2.4.3. Persistent or Recurrent Adverse Events

A persistent AE is one that extends continuously, without resolution, between patient evaluation time points. Such events should only be recorded once on the AE eCRF with the severity (intensity or grade) of the events recorded at the time the event is first reported.

A recurrent AE is one that resolves between patient evaluation time points and subsequently recurs, or notes a change in severity or seriousness. Each recurrence of an AE should be recorded as a separate event on the AE eCRF. For example:

- If Grade 1 vomiting has worsened to Grade 2 five days after onset, the Grade 1 vomiting is resolved on the date when the severity changed, and Grade 2 vomiting is recorded as a new event on the eCRF with onset date reflecting the change in severity.

If non-serious event of neutropenia required hospitalization 5 days after onset, the event is resolved on the hospitalization date, and a new SAE of neutropenia is recorded on the eCRF with start date reflecting when the event required hospitalization.

9.2.4.4. Abnormal Laboratory Values

Not every laboratory abnormality qualifies as an AE. A laboratory test result must be reported as an AE if it meets any of the following criteria:

- Is accompanied by clinical symptoms.
- Results in a change in study treatment (e.g., dosage modification, treatment interruption, or treatment discontinuation).
- Results in a medical intervention (e.g., potassium supplementation for hypokalemia) or a change in concomitant therapy.
- Is clinically significant in the Investigator's judgment.

It is the Investigator's responsibility to review all laboratory findings. Medical and scientific judgment should be exercised in deciding whether an isolated laboratory abnormality should be classified as an AE.

If a clinically significant laboratory abnormality is a sign of a disease or syndrome (e.g., alkaline phosphatase and bilirubin $5 \times$ upper limit of normal [ULN] associated with cholestasis), only the diagnosis (i.e., cholestasis) should be recorded on the AE eCRF.

9.2.4.5. *Abnormal Vital Sign Values*

Not every vital sign abnormality qualifies as an AE. A vital sign result must be reported as an AE if it meets any of the following criteria:

- Is accompanied by clinical symptoms.
- Results in a change in study treatment (e.g., dosage modification, treatment interruption, or treatment discontinuation).
- Results in a medical intervention or a change in concomitant therapy.
- Is clinically significant in the Investigator's judgment.

It is the Investigator's responsibility to review all vital sign findings. Medical and scientific judgment should be exercised in deciding whether an isolated vital sign abnormality should be classified as an AE.

If a clinically significant vital sign abnormality is a sign of a disease or syndrome (e.g., high blood pressure), only the diagnosis (i.e., hypertension) should be recorded on the AE eCRF.

Observations of the same clinically significant vital sign abnormality from visit to visit should only be recorded once on the AE eCRF (Section 9.2.4.3 provides details on recording persistent AEs).

9.2.4.6. *Deaths*

Death should be considered an outcome and not a distinct event. All deaths that occur during the protocol-defined AE period should be reported as SAEs, regardless of attribution to study drug. The event or condition that caused or contributed to the fatal outcome should be recorded as the single medical concept (e.g., septic shock) with a fatal outcome. When the event that led to death cannot be identified (e.g., death of unknown origin) report "unexplained death" as the AE and update it when new information clarifies the event that led to death. Only 1 AE can be reported with a fatal outcome for each patient who dies. Other AEs that continued up to time of death should be reported with an outcome of not recovered/resolved. In the event that the death is attributed solely to natural progression of the underlying bleeding, the event is not reportable and should not be recorded as an AE.

9.2.4.7. *Preexisting Medical Conditions*

A preexisting medical condition should be recorded as an AE only if the frequency, severity, or character of the condition worsens during the study. When recording such events on the AE form, it is important to convey the concept that the preexisting condition has changed by including applicable descriptors (e.g., "more frequent headaches").

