4.2. Exclusion Criteria

If a patient meets any of the following criteria, he or she is *not* eligible to participate:

1. Surgery for which the risk of clinically meaningful uncontrolled or unmanageable bleeding is low.
2. Acute life-threatening bleeding (ISTH criteria [32]) at the time of Screening:
 - a. The patient has acute-overt bleeding that is potentially life-threatening, e.g., with signs or symptoms of hemodynamic compromise, such as severe hypotension, poor skin perfusion, mental confusion, low urine output that cannot be otherwise explained.
 - b. The patient has overt bleeding associated with a fall in hemoglobin level by ≥ 2 g/dL, OR, a hemoglobin ≤ 8 g/dL if no baseline hemoglobin is available.
 - c. The patient has acute bleeding in a critical area or organ, such as pericardial, intracranial, or intraspinal.

3. Any surgical procedure that involves the intraoperative use of systemic, intravascular, unfractionated heparin.
4. Primary procedure being considered for efficacy evaluation is a non-surgical interventional procedure (e.g., skin biopsy, lumbar puncture, cardiac catheterization, endoscopic retrograde cholangio-pancreatography).
5. Expected survival of < 1 month due to comorbidity.
6. Known “Do Not Resuscitate” order or similar advanced directive.
7. The patient has a recent history (within 30 days prior to Screening) of a diagnosed TE as follows: VTE (including DVT, PE, intracardiac thrombus); MI (including asymptomatic troponin elevations); disseminated intravascular coagulation (DIC); acute traumatic coagulopathy; cerebrovascular accident; transient ischemic attack; unstable angina pectoris hospitalization; or severe peripheral vascular disease (see [Appendix B](#) for DIC scoring algorithm).
8. Acute decompensated heart failure or cardiogenic shock at the time of screening (see [Appendix C](#) for cardiogenic shock definition).
9. The patient has sepsis or septic or hemorrhagic shock at the time of Screening (see definition in Appendix C).
10. The patient has heparin-induced thrombocytopenia (with or without thrombosis).
11. Inherited coagulopathy (e.g., anti-phospholipid antibody syndrome, protein C/S deficiency, Factor V Leiden) at time of Screening.
12. Platelet count < 80,000/ μ L at the time of Screening.
13. Last dose of apixaban < 2.5 mg, rivaroxaban < 10 mg, edoxaban < 30 mg, enoxaparin < 40 mg.
14. The patient is pregnant or a lactating female.

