9.1.2. Serious Adverse Events

An SAE is any AE, occurring at any dose and regardless of causality, that:

- Is fatal (i.e., the AE actually causes or leads to death).
- Is life-threatening. Life-threatening means that, in the opinion of the Investigator or Study Sponsor, the patient/subject was at immediate risk of death from the reaction as it occurred, (i.e., it does not include a reaction that hypothetically might have caused death had it occurred in a more severe form).
- Requires inpatient hospitalization or prolongation of existing hospitalization.
- Results in persistent or significant disability/incapacity. Disability is defined as a substantial disruption of a person's ability to conduct normal life functions.

- Is a congenital anomaly/birth defect in a neonate/infant born to a mother who was exposed to study drug or where the father was exposed to study drug before conception.
- Is an important medical event. An important medical event is an event that may jeopardize the patient/subject and may require medical or surgical intervention to prevent one of the outcomes listed in the definitions for SAEs above. Examples of such medical events include allergic bronchospasm requiring intensive treatment in an emergency room or at home, blood dyscrasias or convulsions that do not result in inpatient hospitalization, or the development of drug dependency or drug abuse.

A distinction should be made between the terms “serious” and “severe” since they **are not** synonymous. The term “severe” is often used to describe the intensity (severity) of a specific event (as in mild, moderate, or severe MI); the event itself, however, may be of relatively minor medical significance (such as severe headache). This is **not** the same as “serious,” which is based on the strict regulatory definitions listed above and serves as a guide for defining regulatory reporting obligations. A severe AE does not necessarily need to be considered serious. For example, persistent nausea of several hours duration may be considered severe nausea but not an SAE if the event does not meet the serious criteria. On the other hand, a stroke resulting in only a minor degree of disability may be considered mild but would be defined as an SAE based on the above noted serious criteria. Thus, severity and seriousness need to be independently assessed for each AE recorded on the AE eCRF.

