9.2.1. Adverse Event Reporting Period

To comply with regulatory requirements, all SAEs and non-serious AESIs, regardless of causality, that occur from the date of signing of the ICF until 30 days after the last study drug treatment, must be reported to the Sponsor or its safety designee within 24 hours from Investigator awareness of the event. Survival status and reason for death will be ascertained at the Follow-up Day 30 study visit.

Patients who experience an andexanet-related AE or SAE will be followed until the AE or SAE is resolved or until a new stable baseline is established, even if this occurs after the Follow-up Day 30 visit. All AEs spontaneously reported by the patient and/or in response to an open question from study personnel or revealed by observation, physical examination, or other diagnostic procedures will be recorded and reported on the appropriate eCRF through the Follow-up Day 30 visit.

After informed consent has been obtained **but prior to initiation of study drug**, only SAEs caused by a protocol-mandated intervention (e.g., invasive procedures such as biopsies, discontinuation of medications) should be reported to the Sponsor or safety designee. These pre-dose AEs will be collected on the AE eCRF and assessed as not related to study drug, but will be assessed for relationship to study procedures/tests and interventions.

After initiation of study drug, all TEAEs, regardless of relationship to study drug, will be reported until **30 days after the last dose of study drug**. Any SAE that occurs with an onset date later than 30 days after completion of the study and that the Investigator considers to be related to study medication must be reported to the Sponsor or safety designee.

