10.5. End of Study Assessments

Patients will have their survival status reported by phone on the Day 30 or End of Study visit. This assessment will record the patient's status as alive or provide the date, time, and cause of death. Note: see Section 9.0 for AEs reported for all deaths.

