11.7.3. Deaths

All deaths will be assessed by the EAC. Deaths due to cardiovascular causes (i.e., resulting from MI, sudden cardiac death, heart failure, stroke, cardiovascular procedures, cardiovascular hemorrhage, and other cardiovascular causes) will be classified as related to bleeding or non-hemorrhagic.

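### Section 9.2.4.6 both requires every death in the AE period to be reported as an SAE and exempts deaths attributed solely to natural progression of an undefined underlying bleeding

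*Protocol*

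**What the plan says.** Section 9.2.4.6 (Deaths) opens with a general rule: "All deaths that occur during the protocol-defined AE period should be reported as SAEs, regardless of attribution to study drug". It asks for the causal condition to be recorded as a single event with a fatal outcome, and even a death of unknown cause is to be entered as an AE. It then closes with an exemption: when a "death is attributed solely to natural progression of the underlying bleeding, the event is not reportable and should not be recorded as an AE".

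Other sections bear on the same event:

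- Section 9.1.2 lists as its first seriousness criterion that the AE "Is fatal (i.e., the AE actually causes or leads to death", at any dose and whatever the causality.
- Section 9.2.1 sets 24-hour reporting for "all SAEs and non-serious AESIs, regardless of causality, that occur from the date of signing of the ICF until 30 days"; the 30 days are counted from the final andexanet dose.
- Section 10.5 adds: "Note: see Section 9.0 for AEs reported for all deaths".
- Section 4.2 excludes "Acute life-threatening bleeding (ISTH criteria [32]) at the time of Screening". Section 4.1 makes the need for urgent surgery the qualifying condition.
- Deaths are also captured outside the AE form. Of the Day 30 survival check, Section 10.5 says: "This assessment will record the patient's status as alive or provide the date, time, and cause of death". Section 11.7.3 says: "All deaths will be assessed by the EAC". Section 11.7 makes adjudicated all-cause and cardiovascular mortality within 30 days a safety endpoint.

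**The concern.** A site facing a bleeding death finds opposite instructions in one paragraph. One makes the death an SAE whatever its attribution. The other makes it neither reportable nor an AE if it is put down solely to natural progression of the underlying bleeding.

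The exemption is worded as for a trial in which patients enroll because they are bleeding. Here they enroll because they need surgery, and the protocol does not say what the underlying bleeding would be. The drug is given to support hemostasis during surgery, so a fatal surgical or post-surgical bleed is among the events a safety reader most wants in the serious-event data. If a site took the phrase to cover such a bleed, no AE record would be made of the death and no fatal outcome would be entered. Nor would the 24-hour report of it be triggered. Any omission of this kind makes the AE and SAE tables look better.

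**Working it through.** No arithmetic applies. The point rests on whether the sections can be read together.

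**Step 1: within 9.2.4.6.** The opening rule covers all deaths in the AE period and sets attribution aside. The closing sentence removes a class of deaths, and it does so by attribution of cause. It is not worded as an exception to the rule, and no sentence says which prevails.

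**Step 2: against the AE and SAE definitions.** One could say that the exemption avoids a formal clash with 9.1.2 by declaring the event not to be an AE at all. That fails. Section 9.1.1 counts both a new event and an exacerbation of a previous condition after study drug as AEs, and 9.2.4.7 requires a pre-existing condition to be recorded as an AE when it worsens. Even a bleed already present at entry that then proves fatal meets these definitions. Being fatal, it meets 9.1.2.

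**Step 3: against the reporting rule and Section 10.5.** Section 9.2.1 requires SAEs to reach the sponsor within 24 hours regardless of causality, with no exception by cause of death. The note in 10.5 presumes that Section 9.0 yields an AE for all deaths.

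**Step 4: what the term can refer to.** Exclusion 2 removes bleeding with hemodynamic compromise, overt bleeding with a hemoglobin fall of at least 2 g/dL (or a level of 8 g/dL or less without a baseline value), and bleeding at a critical site. Exclusion 9 removes hemorrhagic shock. Lesser bleeding at entry is not excluded. So the phrase has a narrow literal referent, but few enrolled patients should have an entry bleed likely to kill by natural progression. Surgical and post-surgical bleeding is where a site could misapply it.

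**Step 5: whether anything in the document resolves it.** Administrative Change Letter 1 revises causality and severity categories (9.2.2, 9.2.3) and antibody testing. Letter 2 revises who assesses hemostasis and one exploratory endpoint. The Japan amendments change dosing text and 9.2.2. None touches 9.2.4.6. Letter 1 makes the AE record more important, because it drops the fatal severity grade on the ground that death is collected as an outcome. Without an AE record there is no such outcome field.

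**Step 6: what is lost and what is kept.**

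| Route | Would an exempted death appear? |
|---|---|
| AE/SAE record of the fatal event (9.2.4.6) | Could be missing |
| 24-hour report of the death to the sponsor (9.2.1) | Could be missing |
| Serious TEAE summary, and related TEAE summary if judged related (11.7.1) | Could be missing |
| Day 30 survival status with cause (10.5) | Yes |
| EAC assessment of deaths (11.7.3) | Yes |
| 30-day mortality endpoint (11.7) | Yes |

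Timing matters too. Under Section 11.8, DSMB monitoring starts after 50 patients and then runs about every 6 months. The scheduled survival check is at Day 30.

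**The case against.** The strongest reply is that the trial does not lose sight of the death. Date, time and cause are recorded at Day 30. The EAC assesses every death and classes cardiovascular deaths as related to bleeding or not. It also assesses all potential post-surgical bleeding, and confirmed post-surgical bleeding counts as poor hemostatic efficacy under Section 7.3. This stands. A reader might infer that the exemption hides fatal bleeding from the trial altogether; the documents do not support that.

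A second reply is that the wording is narrow. It requires attribution solely to natural progression of something underlying, which most naturally means bleeding present at entry. New bleeding from an incision fits poorly. This also stands in part: a reader might infer that surgical bleeding is the only bleeding the sentence can reach, but non-life-threatening bleeding at entry is not excluded. The defect is an undefined term open to misapplication. The contradiction remains on the narrow reading, as step 2 shows.

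A third reply is that a serious new bleed is usually an SAE while the patient is still alive, so the 24-hour clock may already be running. That is fair, and it means the exemption would not always leave a blank. It gives no protection when death comes quickly, or when a site takes the sentence to mean that the whole event should not be recorded.

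**Conclusion.** The contradiction is real, is in current text and is not resolved elsewhere in the document. Section 9.2.4.6 conflicts with itself and with 9.1.2, 9.2.1 and 10.5 on whether certain bleeding deaths are SAEs. The consequence is confined to AE/SAE records, prompt reporting to the sponsor, and the serious and related TEAE summaries. Within those, any effect is in the favourable direction. No efficacy endpoint changes, and adjudicated 30-day mortality still counts the death.

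The misapplication to surgical bleeding assumes that some site would read the undefined term that way; the documents do not show that any has.

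No number of affected deaths can be derived. A reader might scale the ANNEXA-4 mortality of 15.3% (54 of 352, Section 1.4.7) to the planned 100 patients, but those patients had acute major bleeding, mostly intracranial, which Section 4.2 excludes here. The 2.3% that Section 3.4.2.1 cites for urgent surgery is all-cause mortality from a surgical database. Neither figure says how many deaths would be attributed solely to bleeding. The case for correction is the integrity of the reporting rule and does not depend on a count.

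**What to change.** Delete the final sentence of 9.2.4.6, so that every death in the protocol-defined AE period is reported as an SAE with the causal event recorded. Leave that period as 9.2.1 sets it. A new window such as consent to Day 30 would create a fresh conflict, because 9.2.1 limits reporting before study drug to SAEs caused by protocol-mandated interventions and otherwise runs to 30 days after the last dose.

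Then reconcile the deaths known from the Day 30 survival data and the EAC against the SAE forms, confirm that none was withheld under the deleted sentence, and obtain late reports where one was.

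The cost is one deleted sentence, sent to sites by administrative letter and carried into the next amendment, plus a short reconciliation of deaths. No endpoint, sample size or visit changes.
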